EFFICACY ENDPOINTS	
Primary efficacy endpoint:
 
The primary efficacy endpoint will be the responder rate at EOS visit.  Responders are defined as patients with either:
 
 
– No change or decrease in the adjusted INCAT disability score and without any change in CIDP treatment between baseline and EOS visit.
 
or
 
– An increase by 1 point in the adjusted INCAT disability score without requirement of any change in CIDP treatment between baseline and EOS visit.
 

EFFICACY ENDPOINTS	
Secondary efficacy endpoints:
 
Main secondary efficacy endpoints:
 
 
– Change from baseline to 24 weeks (Visit V9) and EOS visit in the adjusted INCAT disability score.
 
– Responder rate at 24 weeks (visit V9).
 
– Time to relapse.
 
– Change from baseline to 24 weeks (Visit V9) and EOS visit in the following scores: 
 
▪ Grip strength with the Martin Vigorimeter in both hands;
 
▪ Rasch-built Overall Disability Scale (R-ODS);
 
▪ Medical Research Council (MRC) 12 muscles sum score (0 to 5) and Rasch-modified MRC (0 to 3).
 
 
 
 
Other secondary endpoints:
 
 
– Percentage of patients at 24 weeks (Visit V9) and EOS visit with no requirement of change in CIDP treatment from baseline.
 
– Change from baseline to 24 weeks (Visit V9) and EOS visit in Patient and Investigator Clinical Global Impression (CGI).
 

STUDY No.	PRISM 2 - I10E-1306: Extension of PRISM - I10E-1302

SAFETY ENDPOINTS
	
Safety endpoints:
 
Treatment-emergent adverse events (TEAEs), including serious adverse events (SAEs) from first study drug administration to the EOS visit.
 
Temporally-associated Adverse Events (TAAEs), defined as TEAEs occurring during study drug administration or within 72 hours after the end of infusion.
 
Clinically significant changes from baseline in vital signs and laboratory tests.

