#### **3.1.4. Treatment Period**

Patients meeting all eligibility criteria will receive 1 dose of study drug at 0.5 g/kg over 1 to 2 day(s), every 3 weeks (+/- 7 days) for a total of 16 doses.

Investigators or Study Nurses will call patients 4 days (+/1 day) after the end of each study treatment course to document potential AEs and TAEs (see Section [8.2.2](#)).

Duration of the treatment period will be approximately 45 weeks.

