#### 3.2 HANDLING OF MISSING DATA AND OUTLIERS

Regarding the primary criterion, a patient will be also considered as a non-responder if the patient is withdrawn due to lack of efficacy of the treatment (insufficient response to the investigational medicinal product [IMP]). If the INCAT score at EOS visit is missing, then the Last Observation Carried Forward (LOCF) approach will be applied and the last available adjusted INCAT disability score will replace the missing value at EOS visit.

The LOCF approach will also be used to handle the missing data of secondary endpoints.

When AEs are documented in the diary, date-time of AE onset may be missing or incomplete. As a result, it might not be possible to determine if the AE started between the start of an infusion until 72 hours after the end of the infusion (Temporally Associated AE [TAAE]). In such cases, the response to the question "Did the

AE start within 72 hours of an infusion” will be used for determining if the AE is temporally associated to an infusion or not.

Partial dates of first symptoms and partial dates of diagnosis (collected in the I10E-1302 study) will be imputed by 15 if only the day is unknown and by 1st July if day and month are unknown. No imputation will be done if the year is unknown.

For the calculation of duration of AEs, partial start and end dates will be imputed with the first and last possible date within the period defined by the partial date, respectively. In general, no calculation of duration will be made if either the start date or stop date is missing, i.e., can't be imputed using pre-determined rules.

No other general rules for the replacement of missing data are planned.

Data listings will always show the original CRF reported values and not the imputed values.

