  - TEAE = “Yes” if AE onset date  $>$  start date of first IMP infusion.
  - TEAE = “Yes” if AE onset date = start date of first IMP infusion and investigator’s assessment of the time of onset  $\neq$  “Before infusion”.
  - TEAE = “No” otherwise.
3. If the date of AE onset is a partial date and the investigator’s assessment of the time of onset is not missing: TEAE = “Yes” if investigator’s assessment of the time of onset “During infusion”, “ $\leq 72h$ ” or “ $> 72h$ ”.
4. If the date of AE onset is a partial date and the investigator’s assessment of the time of onset is missing:
  - TEAE = “Yes” if last possible date in the period defined by the partial date  $\geq$  start date of first IMP infusion / “No” if the last possible date in the period defined by the partial date  $<$  start date of first IMP infusion.
5. TEAE = “Yes” otherwise.

A summary of the total number of AEs, and number and percentage of patients with at least one AE will be presented. This summary will include:

- All TEAEs
- TEAEs by seriousness criterion
- TEAEs by drug relationship
- TEAEs by temporal association with infusion (TEAE within the 72h after an infusion Yes/No)
- TEAEs by severity (Mild / Moderate / Severe)
- TEAEs by Action taken with IMP (None / Dose reduced / Dose increased / Discontinuation of IMP / Interruption of IMP)
- TEAEs by outcome (Resolved without sequelae / Resolved with sequelae / Not recovered / Recovering / Fatal / Unknown)

A similar summary table will be produced for TAAEs as well as drug related TEAEs.

All TEAEs, SAEs and drug-related AEs will be summarized by SOC and PT, showing number of TEAEs, and number and percentage of patients with at least one TEAE, sorted by decreasing incidence of SOC and PT within SOC. Summary of TEAEs will also be presented by relevant subgroups (e.g., by age group [using

median as cut point], sex, race [white and non-white]/ethnicity [Hispanic or Latino and not Hispanic or Latino], and BMI [using median as cut point]). The rate of TEAEs by course and by infusion will be calculated as the absolute number of TEAEs divided by the number of courses and number of infusions, respectively and will be presented in the same manner.

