#### Temporally Associated Adverse Events (TAAEs)

The following rules for the derivation of the TAAE status will be used in the order of display.

1. If the exact date-time of the AE onset is known this information will be used: TAAE = "Yes" if AE onset date-time  $\geq$  start date-time of previous IMP infusion and (AE onset date-time – end date-time of previous IMP infusion)  $\leq$  72 hours / "No" otherwise".
2. If the exact date-time of onset is not known and the investigator's assessment of the time of onset is not missing: TAAE = "Yes" if investigator's assessment of AE onset time is either "During infusion" or " $\leq$ 72h" / "No" otherwise".
3. If the exact date-time of onset is not known, the investigator's assessment of the time of onset is missing and the exact date of onset of the AE is known: TAAE = "Yes" if AE onset date is on the same day than an IMP infusion or within 3 days after an infusion / "No" otherwise".
4. TAAE = "No" otherwise.

The same analyses as for TEAEs will be repeated for the TAAEs, i.e. AEs which started within 72 hours of an infusion. For the determination if an AE started within the 72 hours of an infusion the date-time of onset of the AE outweighs the investigator's answer to the question if the AE occurred *Before infusion / During infusion / Within 72 hours after end of infusion / More than 72 hours after end of infusion*. The investigator's answer to this question is only considered for the determination of TAAE if the date-time of AE onset is not precise enough to make a clear decision (i.e. time missing and date on the same date as an infusion or three days after the end of the previous infusion, incomplete date of onset).

The summary table on TAAEs will be presented twice:

- Using the patient as statistical unit
- Using the individual infusion as statistical unit

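### For events with an onset date but no onset time, SAP 4.7.2 gives two incompatible rules for TAAE status, and rule 2 misclassifies a day-2 event ticked as before the infusion

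*SAP*

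**What the plan says.** The protocol synopsis defines TAAEs as "TEAEs occurring during study drug administration or within 72 hours after the end of infusion", and SAP 2.5.3 uses the same 72-hour window. Each patient receives "1 dose of study drug at 0.5 g/kg over 1 to 2 day(s), every 3 weeks" (Protocol 3.1.4), so a course may contain two infusions.

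SAP 3.2 expects gaps in the data: "When AEs are documented in the diary, date-time of AE onset may be missing or incomplete". Where that leaves the 72-hour question open, the investigator's answer is to be used.

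SAP 4.7.2 then sets out four rules: "The following rules for the derivation of the TAAE status will be used in the order of display". In summary:

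- Rule 1: exact date and time known. Measure from the previous infusion.
- Rule 2: opens "If the exact date-time of onset is not known and the" investigator's category is present. The category decides: *During infusion* or *≤72h* is Yes, anything else is No.
- Rule 3: time and category missing, date known. Yes on an infusion day or up to three days after.
- Rule 4: everything else is No.

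The paragraph below the rules says that the category "is only considered for the determination of TAAE if the date-time of AE onset is not precise enough to make a clear decision". It describes those cases as an incomplete date, or a missing time with a date on an infusion day or three days after the previous infusion.

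**The concern.** Rule 2 and the paragraph cannot both be programmed. Rule 2 lets the category decide whenever the time is missing. The paragraph, like SAP 3.2, lets it decide only when the date leaves the question open. Nothing says which governs, so two programmers following the SAP could produce different TAAE tables from the same data.

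The second problem lies in rule 2 itself. *Before infusion* does not say which infusion. On the second day of a two-day course it can be a truthful answer for an event that began after the first infusion, and rule 2 then removes an event that meets the definition.

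TAAEs are a named safety endpoint, tabulated by patient and by infusion. The events these rules must sort are the diary events without times that SAP 3.2 anticipates.

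**Working it through.** **Step 1. Which dates settle the question without a time?** Let *k* be the number of calendar days from the day an infusion ended to the onset date, and *e* the clock hour at which it ended (0 to 24). The onset lies between 24*k* − *e* and 24(*k* + 1) − *e* hours after the end. Over all values of *e* the range is 24(*k* − 1) to 24(*k* + 1).

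| Days after infusion | Hours after its end | Within 72 hours? |
|---|---|---|
| 1 | 0 to 48 | always |
| 2 | 24 to 72 | always |
| 3 | 48 to 96 | date cannot decide |
| 4 or more | 72 upwards | no, apart from the exact midnight limit |

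This matches the paragraph, which lists day 3 as undecided but not days 1, 2, 4 or later.

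**Step 2. Complete date, time missing, category present.** Days are counted from the most recent infusion.

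| Onset date | Category ticked | Rule 2 | Paragraph |
|---|---|---|---|
| Infusion day | any | category decides | same |
| 1 or 2 days after | *During*, *≤72h* | Yes | Yes |
| 1 or 2 days after | *Before*, *>72h* | **No** | **Yes** |
| 3 days after | any | category decides | same |
| 4 or more days after | *During*, *≤72h* | **Yes** | **No** |
| 4 or more days after | *Before*, *>72h* | No | No |

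The conflict is confined to the two bold rows, and they point in opposite directions.

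**Step 3. Day 2 of a course given on two consecutive days.** Here *k* = 1 relative to the day-1 infusion, so any onset is less than 48 hours after that infusion ended and is a TAAE by SAP 2.5.3.

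- Rule 1 (time known): Yes. On an assumed course with infusions from 10:00 to 14:00 on both days, onsets 1, 6, 12 and 19.9 hours after the end of the first infusion all score Yes. A grid of 0.1 hour over 24 days shows no mismatch between rule 1 and the 72-hour definition.
- Rule 3 (time and category missing): Yes.
- Rule 2 (time missing, category present): Yes for *During* or *≤72h*, but No for *Before* or *>72h*.

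The same untimed event is therefore Yes if the category is blank and No if the investigator ticks *Before infusion*. The paragraph does not rescue it, because it also hands every infusion day to the category.

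**Step 4. An error in the other direction.** Rule 3 scores all of day 3 as Yes. With an assumed infusion end at 14:00, day 3 runs from 72 − 14 = 58 to 96 − 14 = 82 hours, so (82 − 72)/24 = 42% of that day is outside the window.

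**Step 5. Scale.** Protocol 5.1 expects 15 to 30 patients and Protocol 6.1.3.1 plans 16 doses: 15 × 16 = 240 to 30 × 16 = 480 courses at most. This is a ceiling on courses, not a count of affected events. SAP 4.10 reports early termination, which lowers it. Neither the share of two-day courses nor the share of untimed events is given.

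**Step 6. A related point in the TEAE rules.** TEAE rule 3 opens "If the date of AE onset is a partial date and the" investigator's category is present, and gives Yes for *During*, *≤72h* or *>72h*. The comparison with the first I10E-1306 infusion comes only in rule 4. As written, a partial date lying wholly before that infusion and ticked *>72h* becomes a TEAE, although the same section defines events before that infusion as I10E-1302 AEs.

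**The case against.** The conflict in step 2 needs data that contradict themselves, and the study has safeguards. The diary asks for the start date and time (Protocol 8.2.1). A call four days after each course is meant to catch TAAEs, with follow-up at the next visit (Protocol 10.2). Consistency checks, queries and a final data review follow (Protocol 11.2). These should make such cases uncommon. They do not say which rule applies to those that remain.

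On day 2, SAP 3.2 and the adverse event variables in SAP 4.7.2 word the question in terms of any infusion, so *≤72h* is an available and correct answer, and nothing shows that investigators would tick *Before infusion*. That is fair as to frequency. It does not repair rule 2, which gives a wrong result for an answer that can be truthful.

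A reader might go further and infer that the rules score events between two infusions as No in general, and so undercount infusion-related events. The documents do not support this. Rules 1 and 3 score such events Yes, the conflict between rule 2 and the paragraph runs both ways, and rule 3 can overcount on day 3. Rule 4's default of No, against a default of Yes for TEAEs, might also look like a fault. It is reached only when the date is incomplete and the category is missing, and the two windows differ so much in length that different defaults are a matter of preference.

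The TEAE case is remote for events collected in this study. Collection starts at consent (Protocol 9.5.3), and inclusion is within 72 hours of the I10E-1302 final visit (Protocol 3.1.1). A date with the day unknown would need a month boundary in that short gap.

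**Conclusion.** The point stands in two parts. SAP 4.7.2 contradicts itself, and its rule 2 contradicts SAP 3.2, for an untimed event whose category disagrees with a decisive date. Rule 2 is also wrong for an untimed day-2 event ticked *Before infusion*. Both affect the reproducibility of a named safety endpoint and should be corrected before database lock.

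The number of events affected and the net direction cannot be determined from the documents. A misfiled event need not change a patient-level count if the patient has another TAAE, and it still appears in the TEAE tables.

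The day-2 result assumes that a two-day course runs on consecutive days and that the first infusion ends on the day it starts. Apart from that, steps 1 to 3 do not depend on clock times; the 42% in step 4 does. The TEAE ordering is a minor consistency point.

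**What to change.** Restrict rule 2 so that, for a complete date without a time:

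1. A date one or two days after any infusion is Yes. This includes day 2 of a course, whatever category is ticked, and takes precedence over the points below.
2. A date four or more days after the last infusion is No.
3. Otherwise, meaning the day of a course's first infusion or three days after the last infusion, the investigator's category decides, and rule 3 still applies when the category is missing.

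Incomplete dates continue to use the investigator's category, and rule 4 stays as it is. Amend the paragraph below the rules so that its list of undecided dates no longer includes day 2 of a course.

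In the TEAE rules, check before rule 3 whether the last possible onset date precedes the first I10E-1306 infusion. If it does, the event is not a TEAE.

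The cost is a small amount of SAP wording and programming. TAAE counts may move slightly in either direction.

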#### 4.7.3 Other Safety Endpoints

Unless otherwise specified, the baseline value is defined as the last available value before the first IMP course in I10E-1306. The baseline value might therefore come either from the last visit in the I10E-1302 study or the first visit in the I10E-1306 study.

- Laboratory data

All laboratory values will be reported in standard international (SI) units. Summary displays for laboratory safety data (hematology and chemistry) will be produced by visit for both observed and change from baseline values of the different laboratory analyses. Laboratory tests taken only at screening, those in case of a qualifying event (e.g., thrombosis or haemolysis), and urine protein reagent strip test results will be presented in the laboratory listings. The following clinical parameters will be summarized:

##### Hematology:

- Complete blood count + differentials, hemoglobin (Hb), mean corpuscular volume (MCV), platelets count
- Haptoglobin

##### Biochemistry:

- Creatinemia, glomerular filtration rate according to MDRD
- LDH
- Total and free bilirubin (total bilirubin in all patients; if total bilirubin > ULN, free bilirubin will be assessed from the same blood sample, as total bilirubin)
- AST, ALT, alkaline phosphatase (ALP),  $\gamma$ GT
- Total serum protein level
- Serum IgA levels

Laboratory values will be classified as normal, low, or high based on standardized normal ranges. Laboratory categories will be expressed in terms of the L (below lower limit of normal [LLN]), N (between LLN and ULN) and H (above ULN) classifications for numerical measurements and normal, abnormal for categorical measurements. The number and percentage of patients with abnormal values

will be summarized for each laboratory parameter by visit. These summaries will include the number and percentage of patients with “any pre-treatment visit” and “any on-treatment visit post baseline” abnormality for each parameter. These displays will ensure that all abnormal values will be captured.

LNH shifts in clinical laboratory values (hematology and chemistry) from baseline to each visit post first dosing will be summarized by visit. Patients with values outside the normal range will be flagged.

#### Hy's Law, Temple's Corollary and Elevated Liver Function Test (LFT) Results

Incidence of patients with liver function test results satisfying the drug-induced liver injury (DILI) criterion defined as ( $> 3xULN$  for ALT/AST,  $> 2xULN$  for total bilirubin and  $\leq 2xULN$  for ALP at the same time-point) will be presented by visit. According to Hy's Law, a pure DILI case leading to jaundice, without a hepatic transplant, has a case fatality rate of 10% to 50%.

Incidence of patients with liver function test results satisfying Temple's criterion defined as ( $> 3xULN$  for ALT/AST,  $\leq 2xULN$  for total bilirubin and  $\leq 2xULN$  for ALP at the same time-point) will be presented by visit.

In addition, incidence of elevated liver function test results will be presented at each visit by elevation criterion. Elevation criteria are given as follows:

- ALT (ULN -  $\leq 3xULN$ ,  $> 3xULN - \leq 5xULN$ ,  $> 5xULN$ )
- AST (ULN -  $\leq 3xULN$ ,  $> 3xULN - \leq 5xULN$ ,  $> 5xULN$ )
- Total Bilirubin (ULN -  $\leq 2xULN$ ,  $> 2xULN$ )
- ALP (ULN -  $\leq 2xULN$ ,  $> 2xULN$ )

A scatter plot of the values at the EOS assessment as well as the minimum and maximum values of each patient during the treatment follow-up against the values at baseline will be prepared for each parameter. The first diagonal will be displayed by a dotted line.

Laboratory test results will be listed, including all abnormalities, clinically significant or not. Pregnancy status and test results will also be listed, including the method of contraception used (if any).

- Vital Signs

Vital signs parameters including systolic and diastolic blood pressure (mmHg), heart rate (bpm), weight, and body temperature ( $^{\circ}C$ ) (calculated value according to the way the temperature was measured) will be summarized.

- Patient level analyses

Descriptive statistics of vital sign values will be presented for the following time points.

- a) Visit 1 may be taken from (I10E-1302)
- b) Before first infusion
- c) 30-45 min and 60-75 min after the start of the first infusion
- d) 30-45 min after the end of the first infusion
- e) EOS

Change from time point b) will be presented for time points c) to e). The minimum and maximum of each parameter during the patient's treatment follow-up will be presented.

A scatter plot of the values at the end of study assessment as well as the minimum and maximum values of each patient during the treatment follow-up against the values at baseline will be prepared for each parameter. The first diagonal will be displayed by a dotted line.

- Infusion level analyses

Vital sign results will be presented in listings using the following time points.

- a) Before the start of the course (only first infusion of a course)
- b) 30-45 min and 60-75 min after the start of the infusion
- c) 30-45 min after the end of the infusion

The listings will also include change from before start of the course to time points b) and c).

All abnormalities, clinically significant or not, will be listed in both patient level and course/infusion level formats.

- Thrombo-embolic physical examination

Number and percentage of patients with at least one abnormal thrombo-embolic sign will be presented by visit together with the absolute number of signs for the following:

- Arterial thrombo-embolic signs
- Venous thrombo-embolic signs

- Complete physical examination

Physical examination results will be listed.

#### 4.8 PHARMACOKINETICS

Not Applicable.

#### 4.9 EXPLORATORY ANALYSES

The following exploratory endpoints will be listed by visit using FAS.

- 1) Anti-CNTN1 and anti-NF155 antibodies titers at EOS visit
- 2) BAFF and complement components (C3 and C4 antigens, CH50) at EOS visit
- 3) Serum total IgG trough levels at least 24 hours prior each study drug administration

In addition, a listing of patients included in the ultrasonography ancillary study will be provided. The listing will include information on the consent date for the ancillary study and whether data were collected (Yes/No).

#### 4.10 CHANGES IN THE CONDUCT OF THE STUDY OR PLANNED ANALYSIS

Early assessment of study results showed a remarkable percentage of patients who demonstrate CIDP relapse at the tested lower dose. It was decided then to early terminate the study in the interest of the patients and according to good clinical practices. This rationalized the presentation of the efficacy results to focus on key efficacy endpoints.

Results for response rate at 24 weeks, MRC 12 muscles sum score, Rasch-modified MRC sum score, Percentage of patients without change in CIDP treatment from baseline to 24 weeks and EOS visit, and patient and investigator CGI will be presented in listings.

Patient level and course/infusion level information will be provided for exposure, laboratory, and vital signs parameters.

Analysis of laboratory data may involve standardization procedure contingent on the evaluation of the sparseness of laboratory data, the completeness of the local laboratories' normal ranges, and the choice of the standard normal ranges prior to database lock. Liver function test results will be examined to identify Hy's Law, Temple's Corollary, and elevated test result cases.

Analysis of biomarker data will not be performed. Instead the data will be listed using FAS.

Planned analysis associated with the ultrasonography ancillary study will not be performed due to non-collection of required data.

